## 6. ANALYSES AND SUMMARIES

Separate tables will be produced for **Part 1: SAD** and **Part 2: MAD** unless otherwise specified. Listings will include both Part 1: SAD and Part 2: MAD unless otherwise specified. Placebo will be reported separately by Cohort for **Part 1: SAD**. If doses have been repeated, data will be pooled unless otherwise specified.

### 6.1. Primary Endpoint(s)

#### 6.1.1. Adverse Events

Adverse events will be reported in accordance with the sponsor reporting standards.

#### 6.1.2. Laboratory Data

Laboratory data will be listed and summarized by treatment in accordance with the sponsor reporting standards. Baseline is as defined in [Section 3.1.2](#).

A listing of the most clinically significant laboratory test abnormalities, by participant will be produced. The listing will include the baseline value, most abnormal value and the final value.

#### 6.1.3. Vital Signs

Absolute values and changes from baseline in supine systolic and diastolic blood pressure, pulse rate, temperature and respiratory rate will be summarized by treatment and time post-dose, according to sponsor reporting standards. Tables will be paged by parameter. Baseline is as defined in [Section 3.1.3](#).

Mean changes from baseline for supine systolic and diastolic blood pressure, pulse rate, temperature and respiratory rate will be plotted against time post-dose. On each plot there will be 1 line for each treatment. Data from all cohorts will be plotted on the same figure using separate lines for each placebo for Part 1: SAD and a single line for the pooled placebo for Part 2: MAD. Corresponding individual plots of changes from baseline will also be produced for each treatment.

Maximum decrease from baseline for supine systolic and diastolic blood pressures and respiratory rate and maximum increase from baseline for supine pulse rate and temperature will be summarized by treatment, according to sponsor reporting standards.

Maximum absolute values and changes from baseline for supine vital signs will also be summarized descriptively by treatment using categories as defined in [Appendix 1](#). Numbers and percentages of participants meeting the categorical criteria will be provided. All planned and unplanned post-dose timepoints will be counted in these categorical summaries.

#### 6.1.4. ECG

Absolute values and changes from baseline in QT, heart rate, QTcF, PR and QRS will be summarized by treatment and time post-dose using sponsor reporting standards. Tables will be paged by parameter. Baseline is as defined in [Section 3.1.4](#).

Mean changes from baseline in QT, heart rate and QTcF will be plotted against time postdose. On each plot there will be 1 line for each treatment. Data from all cohorts will be plotted on the same figure using separate lines for each placebo for Part 1: SAD and a single line for the pooled placebo for Part 2: MAD. Corresponding individual plots of changes from baseline will also be produced for each treatment.

Changes from baseline in QTcF will also be plotted separately against drug concentrations (separate plots for PF-07304814 and PF-00835231). This will be a scatter plot for all observations where QTcF and drug concentration are recorded. Placebo data will also be included (with drug concentration set to zero). Different symbols will be used for each treatment.

Maximum increase from baseline for QTcF will be summarized by treatment, according to sponsor reporting standards.

ECG endpoints and changes from baseline (QTcF, PR and QRS) will also be summarized descriptively by treatment using categories as defined in [Appendix 1](#) (for QTcF these correspond to the Pfizer Guidance in [Section 8](#)). Numbers and percentages of participants meeting the categorical criteria will be provided. All planned and unplanned postdose timepoints will be counted in these categorical summaries.

Listings of participants with any single post-dose value >500msec will also be produced for QTcF.

#### **6.1.5. Pulse Oximetry/SpO2**

Absolute values and changes from baseline in pulse oximetry/SpO2 will be summarized by treatment and time post-dose. Baseline is as defined in [Section 3.1.5](#).

Numbers and percentages of participants meeting the categorical criteria as defined in [Appendix 1](#) will be provided. All planned and unplanned post-dose timepoints will be counted in these categorical summaries.

All tables above will have three columns per treatment based on whether the participant is receiving oxygen CCI throughout, at somepoint during the study or never received. Days 2 to 6 will be used i.e. Days 2, 3 & 6 for Part 1: SAD and Days 2, 3, 4, 5 & 6 for Part 2: MAD and any unplanned readings between Day 2 and Day 6 will be used (where collected).

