- j. Administration starts on Day 1 and continues for 24 hours and ends on Day 2. **Sentinel dosing will be used in each dose-escalating cohort.** A small cohort of 2 participants (1 receiving PF-07304814 and 1 receiving placebo) will be dosed prior to the remainder of the cohort. All available safety and tolerability data from the 2 sentinel participants up to Day 3 at 24 hours post completion of dosing will be reviewed by the Investigator(s) (if available), the study team and IRC. The independent IRC will then determine whether it is safe to proceed to dose the remaining participants in the cohort.

k. For discharged participants, Days 6 and 30-37 should be conducted at the clinical site. However, if this is not possible, the visit may be conducted by phone in which case only clinical data (AE, **CCI** [REDACTED] concomitant medications) and contraception check will be obtained. (If available, kits to assess viral load to be provided for at-home specimen collection in the instance that a visit is conducted by telephone, and arrangements may be made to collect blood samples for clinical chemistry and/or hematology).

[REDACTED]

[REDACTED]

PART 2: MAD (120-h infusion)

Visit Identifier	Screening Days -3 to 1	Treatment Day 1	Treatment Days 2-5	End of Treatment Day 6	Follow-up 1 (Day 7)	Follow-up 2 (Day 10) ^l ±1 day	Follow-up 3 (Day 14) ^l ±2 days	Follow-up 4 (Day 34-41) ^l	Early Termination
Planned Hours Post Start of Infusion		pre-Dose	24h (Day 2), 48h (Day 3), 72h (Day 4), 96h (Day 5)	120h					
ELIGIBILITY									
Informed consent	X								
Verify inclusion/exclusion criteria ^a	X								
Demographics & Medical history	X								
Required Confinement		X	→	→	X				
PHYSICAL EXAMINATION & ECG & VITALS									
Complete physical examination	X			X					X
Targeted physical examination		X	X		X	X	X	X	
Supine vital signs (temperature, pulse rate, blood pressure, respiratory rate)	X	X	X	X	X	X	X	X	X
Pulse oximetry/SpO ₂	X	X	X	X	X	X	X	X	X
Weight, Height	X								
12-Lead ECG ^b	X	X	Day 2, 3, 5 only	X	X	X	X	X	X
LABORATORY									
Hematology ^c	X	X	Day 2, 3, 5 only	X	X	X	X	X	X
Blood chemistry ^c	X	X ^d	Day 2, 3, 5 only	X ^d	X	X	X	X	X
Coagulation Panel (PT, aPTT, D-dimer) and Fibrinogen		X	Day 2, 3, 5 only	X	X	X	X	X	X
Urinalysis ^c	X	X	Day 3 only	X	X	X	X	X	X
FSH (to confirm post-menopausal status)	X								
Pregnancy test (WOCBP only)	X ^{c,e}						X		
CCI									
SARS-CoV-2 Viral load Assessments ^f	X	X	Day 3 only	X	X	X	X	X	X

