2.2.2. Clinical Overview

C4611001 is the first clinical study using PF-07304814, and is designed to establish PK, safety and tolerability in a hospitalized COVID-19 population. In order to evaluate these parameters in a more homogeneous healthy population, an additional Phase 1 study, C4611007, is initiated and ongoing. Following the establishment of PK, safety and

tolerability of 24h and 120h infusions of PF-07304814 in these populations, the sponsor proposes a Phase 2/3 adaptive design efficacy study in hospitalized COVID-19 patients (C4611002).

As of 18 November, 2020, 4 patient participants in Cohort 1 received a single dose of PF-07304814 or placebo, administered as a 24-hour continuous IV infusion in the study C4611001. Based on emerging PK data in participants who received PF-07304814, dosing in Cohort 1 (500 mg dose) was stopped and dosing in a new cohort, Cohort 3, at 250 mg was initiated. As of 16 December, 2020, three participants in Cohort 3 have been dosed with either PF-07304814 or placebo.

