6.3. Measures to Minimize Bias: Randomization and Blinding

6.3.1. Allocation to Study Intervention

Allocation of participants to treatment groups will proceed through the use of an IRT system. The site personnel (study coordinator or specified designee) will be required to enter or select information including but not limited to the user's ID and password, the protocol number, and the participant number. The site personnel will then be provided with a treatment assignment, randomization number. The IRT system will provide a confirmation report containing the participant number and randomization number. The confirmation report must be stored in the site's files.

Study intervention will be administered by continuous infusion starting on Day 1 as summarized in the [SoA](#).

The study-specific IRT reference manual and IP manual will provide the contact information and further details on the use of the IRT system.

Participants in each cohort will be assigned to receive study intervention according to randomization scheme. Investigators will remain blinded to each participant's assigned study intervention throughout the course of the study. In order to maintain this blind, an otherwise uninvolved third party will be responsible for the preparation and dispensing of all study intervention and will endeavor to ensure that there are no differences in time taken to dispense or visual presentation following randomization.

In the event of a Quality Assurance audit, the auditor(s) will be allowed access to unblinded study intervention records at the site(s) to verify that randomization/dispensing has been done accurately.

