### **5.2. General Methods**

Unless otherwise stated, all summaries and plots will be presented by treatment. Screening and Early Termination will be included in the summaries.

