#### **5.2.1. Analyses for Continuous Endpoints**

Continuous variables will be presented using summary statistics: number of observations, arithmetic mean, standard deviation, median, minimum and maximum values.

Log transformed continuous variables will be presented using summary statistics: number of observations, arithmetic mean, median, cv%, standard deviation, minimum, maximum, geometric mean and geometric cv%.

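### SpO2 is tabulated only by oxygen use on Days 2 to 6, with no all-participants column; separately, respiratory rate has no per-participant summary of a rise (minor)

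*SAP*

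**What the plan says.** **SpO2.** Change from baseline in pulse oximetry/SpO2 is in the primary endpoint list (Protocol 3, SAP 2.1). SAP 6.1.5 plans absolute values, changes from baseline and the number of participants below the Appendix 1 threshold of 94%. It then sets the layout: "All tables above will have three columns per treatment based on whether the participant is receiving oxygen" and, after a short redaction, "throughout, at somepoint during the study or never received. Days 2 to 6 will be used". No total column and no SpO2 plot are named.

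The general rule in SAP 5.2 is "Unless otherwise stated, all summaries and plots will be presented by treatment. Screening and Early Termination will be included in the summaries". Because that default gives way where a section says something else, it does not supply a total column here.

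**Timing.** For both parts, Protocol 6.3.1 says "Study intervention will be administered by continuous infusion starting on Day 1". For Part 1, the Schedule of Activities adds "Administration starts on Day 1 and continues for 24 hours and ends on Day 2".

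**Group sizes.** Cohorts are about 8 participants, 6 active and 2 placebo (Protocol 9.2). In Part 1, "Placebo will be reported separately by Cohort" (SAP 6). Cohort 1 was stopped early; as of 18 November 2020, "4 patient participants in Cohort 1 received a single dose of PF-07304814 or placebo" (Protocol 2.2.2).

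**Respiratory rate.** SAP 3.1.3 and 6.1.3 derive the maximum decrease for blood pressures and respiratory rate, and the maximum increase for pulse rate and temperature. Under 3.1.3, a participant with no decrease is assigned the smallest increase. Appendix 1 has no respiratory rate row.

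**The concern.** Oxygen use on Days 2 to 6 is observed after treatment has begun. If the drug lowers or raises oxygenation, it can change who needs oxygen and therefore who sits in each column. Active and placebo participants in the same column are then no longer the groups that randomization formed. A table with only those columns gives the reader no direct view of SpO2 by assigned treatment, whereas vital signs and ECG (SAP 6.1.3, 6.1.4) both have unsplit by-treatment tables and plots.

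The respiratory rate point concerns the other direct measure of breathing among the primary safety endpoints. The planned extreme looks only downwards, while a rise is also of interest in a population that Protocol 2.2 describes as at risk of ARDS.

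**Working it through.** **1. Which days classify, and when dosing starts.** Classification uses Days 2, 3 and 6 in Part 1 and Days 2 to 6 in Part 2, plus unplanned readings in that span. Infusion starts on Day 1. Every classifying day therefore follows the start of treatment.

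**2. How thin the columns are.** The plan's own total reproduces: (2 + 3) × 8 + (2 + 2) × 8 = 40 + 32 = 72.
- Active, full cohort: 6 participants in 3 columns, an average of 6/3 = 2.
- Placebo, one Part 1 cohort: 2 participants in 3 columns, so at least 3 − 2 = 1 is empty.
- Cohort 1, with 4 participants at that date: 2 treatments × 3 = 6 columns, at most 4 filled and at least 2 empty.

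**3. What can be rebuilt.** SAP 5.2.1 gives, for each column, "number of observations, arithmetic mean, standard deviation, median, minimum and maximum values". With column sizes nᵢ, means mᵢ and SDs sᵢ:
- N = Σnᵢ, and counts below 94% add.
- Overall mean M = Σnᵢmᵢ / N.
- Overall SD = √{[Σ(nᵢ − 1)sᵢ² + Σnᵢ(mᵢ − M)²] / (N − 1)}, where a column with nᵢ = 1 contributes zero to the first sum.
- Overall minimum and maximum are the extremes of the column values.

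Medians do not add, but small columns can be resolved into individual values. I listed every set of whole-number SpO2 values from 85 to 100, assuming the mean is printed to 1 decimal. With SD to 2 decimals, no two sets of size 2, 3, 4 or 5 share the same mean, SD, median, minimum and maximum. With SD to 1 decimal, a few sets of 4 or 5 do. A column holding all 6 active participants of a cohort is the whole arm, so its median is already the overall one. A real loss is confined to larger pooled groups, such as repeated doses or pooled Part 2 placebo.

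**4. How treatment could move column membership (illustration only).** The documents give no oxygen-use rates. Assume baseline SpO2 with mean 96 and SD 2, visit noise with SD 1.5, and oxygen given below 94. The post-dose SD is √(2² + 1.5²) = 2.5. For a treatment-caused fall of d points, the share on oxygen is Φ((94 − 96 + d)/2.5):

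| d | share on oxygen |
|---|---|
| 0 | 21% |
| 1 | 34% |
| 2 | 50% |
| 3 | 66% |

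In a simulation of the same set-up, a 3-point fall moved the never-oxygen column's mean change from +0.33 to −2.04, a shift of 2.37. The all-participants mean moved from +0.42 to −1.69 (shift 2.11) if oxygen adds 2 points, or from +0.64 to −1.03 (shift 1.67) if it adds 3. Neither display shows the full 3 points. The pooled one hides more, which is why it should supplement the split and not replace it.

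**5. Vital signs with a per-participant summary of a rise.**

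| Vital sign | Summary of a rise |
|---|---|
| Pulse rate | maximum increase; maximum above 120 supine |
| Temperature | maximum increase |
| Systolic BP | increase of 30 or more (Appendix 1) |
| Diastolic BP | increase of 20 or more (Appendix 1) |
| Respiratory rate | none |

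That is 4 of 5 covered. As an example of the 3.1.3 rule, changes of +2, +10 and +14 breaths/min give a maximum decrease of min(+2, +10, +14) = +2. The largest rise, +14, is 12 higher and enters no per-participant summary.

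**The case against.** The strongest reply is that this is a small descriptive study. It has no estimands or hypotheses (Protocol 9.1), no formal safety analysis (Protocol 9.4.1) and no decision rules (SAP 5.1). Escalation relies on ongoing review of emerging data (Protocol 6.6.1), not on these tables. Grouping on a post-baseline variable biases an estimated effect, but none is estimated. SpO2 is also hard to read without oxygen status, so the split is a sensible display. In Part 1 the scheduled post-dose readings fall on exactly the classifying days. Most overall statistics can be recovered, as step 3 shows. On respiratory rate, +2 is the correct value of a statistic labelled maximum decrease. By-time tables show the largest change at each visit, and individual plots show each participant's changes.

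Most of this stands, and it is why the point is minor. Two things remain. The trial is randomized and placebo-controlled, so a reader will compare the treatment columns and should not have to rebuild the by-treatment result by hand for a primary safety measure. And nothing in the plan gives a reason why respiratory rate alone lacks a summary of a rise.

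Text after the words on receiving oxygen is redacted and cannot be read. The visible wording nevertheless fixes the number of columns at three.

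**Conclusion.** The point holds as a minor presentation weakness. All planned SpO2 tables are split by a variable measured after treatment starts, with no all-participants column. Respiratory rate is the only one of five vital signs with no per-participant summary of a rise. The size of any effect on SpO2 results is unknown; the figures in step 4 rest on assumed values and show the mechanism only.

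A reader might infer more than the documents support:
- **That an SpO2 effect would be concealed or would mislead dose decisions.** Most overall results can be recovered, and no rule uses these tables.
- **That the label window is itself a defect.** The SAP states that Days 2 to 6 are used, so it follows that the label does not describe later Part 2 readings. A Part 1 Day 6 visit held on Day 7 under the ±1 day allowance is still the nominal Day 6 reading.
- **That the split must instead use pre-dose oxygen status.** Whether that status is collected cannot be told because of the redaction, and it would not describe oxygen use at the post-dose readings.
- **That respiratory rate rises go unseen.** They remain in the by-time tables and individual plots.

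**What to change.** 1. In SAP 6.1.5, add an all-participants column per treatment to each SpO2 table. Keep the three oxygen-use columns, and add a footnote that the new column mixes readings on and off oxygen.
2. In SAP 3.1.3 and 6.1.3, add maximum increase from baseline in respiratory rate.

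A full cohort's added columns would hold 6 active and 2 placebo participants. Both changes use data already collected and need only SAP wording, one more column per treatment and one more derived value. The downsides are wider tables that still contain small or empty oxygen-use columns, and a pooled SpO2 mean in which oxygen can mask a fall; the footnote and the retained split address the second.

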#### **6.2. Secondary Endpoint(s)**

To assess the pharmacokinetics of PF-07304814 and PF-00835231, the PK parameters detailed in [Section 3.2](#) will be listed and summarized for participants in the PK analysis set (as defined in [Section 4](#)). Missing values will be handled as detailed in Section 5.3. Each PK parameter will be summarized by analyte and dose. Each summary will include the set of summary statistics as specified in Table 4 for the **Part 1: SAD** part and Table 5 for the **Part 2: MAD** part respectively.

**Table 4. PK Parameters to be Summarized Descriptively for Part 1: SAD**

| Parameter  | Dose       | Summary Statistics   |
|--|------------|--|
| $C_{24}$   | All doses  | N, arithmetic mean, median, cv%, standard deviation, minimum, maximum, geometric mean and geometric cv%. |
| $AUC_{last}$ , $AUC_{inf}$ , $C_{24}$ , $C_{ss}$ , $C_{max}$ , CL and $V_{ss}$ | 500mg only | N, arithmetic mean, median, cv%, standard deviation, minimum, maximum, geometric mean and geometric cv%. |
| $t_{1/2}$  | 500mg only | N, arithmetic mean, median, cv%, standard deviation, minimum, maximum.                                   |

**Table 5. PK Parameters to be Summarized Descriptively for Part 2: MAD**

| Parameter   | Summary Statistics   |
|---|--|
| $C_{120}$ , $C_{max}$ , $T_{max}$ , $C_{ss}$ , $C_{120}$ (dn) and $C_{ss}$ (dn) | N, arithmetic mean, median, cv%, standard deviation, minimum, maximum, geometric mean and geometric cv%. |
| $t_{1/2}$   | N, arithmetic mean, median, cv%, standard deviation, minimum, maximum.                                   |

There will be one summary table for each analyte presenting all PK parameters. This will include data from all cohorts and will be presented by dose.

To assess the relationship between the PK parameters and dose, dose normalized  $C_{120}$  and  $C_{ss}$  (**Part 2: MAD**) of PF-07304814 and PF-00835231 will be plotted against dose (using a logarithmic scale), and will include individual participant values and the geometric means for each dose. Geometric means will have a different symbol than the individual values. The values will be dose normalized (to a 1 mg dose) by dividing the individual values and raw geometric means by dose. A footnote will be added to the plots to indicate that geometric means are presented and that data from all cohorts are presented on the plot. Dose normalized  $C_{120}$  and  $C_{ss}$  (**Part 2: MAD**) for both analytes will be listed along with other individual PK parameters.

Supporting data from the estimation of  $t_{1/2}$  will be listed by analyte and dose where applicable: terminal phase rate constant ( $k_{el}$ ); goodness of fit statistic from the log-linear regression ( $r^2$ ); the percent of  $AUC_{inf}$  based on extrapolation ( $AUC_{extrap\%}$ ); and the first, last, and number of time points used in the estimation of  $k_{el}$ . These data may be included in the CSR.

Presentations for PF-07304814 and PF-00835231 concentrations will be presented by analyte using participants in the PK concentration analysis set (as defined in Section 4) will include:

- a listing of all concentrations sorted by participant ID, dose and nominal time post-dose. The concentration listing will also include the actual times. Deviations from the nominal time will be given in a separate listing.
- a summary of concentrations by dose and nominal time post-dose, where the set of statistics will include n, mean, median, standard deviation, coefficient of variation (cv), minimum, maximum and the number of concentrations above the lower limit of quantification.
- individual concentration-time plots by dose (on both linear and semi-log scales) against actual time post-dose (there will be separate spaghetti plots for each dose per scale).
- median concentrations-time plots (on both linear and semi-log scales) against nominal time post-dose by dose (all doses on the same plot per scale, based on the summary of concentrations by dose and time post-dose).
- mean concentrations-time plots (on both linear and semi-log scales) against nominal time post-dose by dose (all doses on the same plot per scale, based on the summary of concentrations by dose and time post-dose).

The scale used for the x-axis (time) of these plots will be decided on review of the data, and will depend on how long PF-07304814 and PF-00835231 concentration is quantifiable in the matrix.

For summary statistics, median and mean plots by sampling time, the nominal PK sampling time will be used, for individual participant plots by time, the actual PK sampling time will be used.

